## List of Abbreviations

AE	Adverse event
ALS	Advanced life support
CABG	Coronary artery bypass graft
CI	Confidence interval
CRF	Case report form
ECG	Electrocardiogram
ED	Emergency department
EMS	Emergency medical services
FDA	Food and Drug Administration
HIPAA	Health Insurance Portability and Accountability Act
ID	Identifier
IDE	Investigational device exemption
IEC	International Electrotechnical Commission
IRB	Institutional Review Board
LED	Light-emitting diode
MI	Myocardial infarction
NIH	National Institutes of Health
OCES	Orange County Emergency Services
PCI	Percutaneous coronary intervention
PHI	Protected health information
PI	Principal Investigator
REDCap	Research Electronic Data Capture
RIC	Remote ischemic conditioning
RCT	Randomized controlled trial
SAE	Serious adverse event
SBP	Systolic blood pressure
SC	Study coordinator
STEMI	ST-segment elevation myocardial infarction
TraCS	Translational and Clinical Sciences
UNC	University of North Carolina

## Study Summary

Title	A pilot study of the feasibility of prehospital delivery of remote ischemic conditioning by emergency medical services in chest pain patients
Short Title	Prehospital RIC Pilot Study
Protocol Number	N/A
Phase	Pilot
Methodology	Open label; Non-randomized; Single-arm
Study Duration	12 months
Study Center(s)	Single-center
Objectives	To assess the feasibility of the delivery of RIC by EMS in the prehospital setting by evaluating the following: Primary outcome – Duration of RIC administered Secondary outcomes – Enrollment rates and protocol efficiency; paramedic acceptability of protocol; and patient tolerability of RIC
Number of Subjects	50
Diagnosis and Main Inclusion Criteria	Patients experiencing a recent onset of chest pain or anginal equivalent symptoms requiring emergency medical services (suspected ST segment-elevation myocardial infarction patients will be excluded)
Study Product, Dose, Route, Regimen	The autoRIC® Device; an upper arm cuff will automatically alternate 5 minutes inflated at 200 mm Hg and 5 minutes deflated for a total of 4 cycles (total 40 minutes)
Duration of administration	40 minutes (4 cycles at 10 minutes each)
Reference therapy	No comparison therapy
Statistical Methodology	Descriptive statistics (e.g., proportions, medians) will be computed to summarize primary and secondary outcomes. Where appropriate, point estimates will be presented along with 95% confidence intervals. No inferential statistical tests will be performed. Qualitative data will be analyzed using mixed methods approaches.

## 1 Introduction

This document is a protocol for a human research study. This study is to be conducted according to US and international standards of Good Clinical Practice (FDA Title 21 part 312 and International Conference on Harmonization guidelines), applicable government regulations and Institutional research policies and procedures.

### 1.1 Background

A myocardial infarction (MI), otherwise known as a heart attack, occurs when obstruction of a coronary artery causes sudden loss of blood flow to the heart muscle. If blood flow is not restored (reperfusion) within the first few hours, the lack of oxygen supply (ischemia) results in irreversible myocardial injury and eventually necrosis of heart tissue (infarction). Depending on the extent of tissue damage, or myocardial infarct size, the individual may die or suffer long-term disabilities. In the U.S., there are ~750,000 MIs each year and ~117,000 related deaths, making it a leading cause of morbidity and mortality. Furthermore, the annual health care costs of myocardial infarction in the U.S. are projected to exceed \$300 billion by 2030.

Prompt reperfusion with emergency coronary stent placement, or primary percutaneous coronary intervention (PCI), substantially reduces myocardial injury and improves clinical outcomes; primary PCI is therefore the preferred treatment for many acute MI patients. However, reperfusion can paradoxically induce further myocardial damage. This ischemia-reperfusion injury can account for up to 50% of the final infarct size in patients with MI following reperfusion. While primary PCI is now the standard of care in the US and other developed countries, therapies to protect against ischemia-reperfusion injury remain investigational.

Remote ischemic conditioning (RIC) is a non-pharmacological and non-invasive therapy for acute MI whereby intermittent, brief episodes of benign ischemia and reperfusion are induced by inflating and deflating a standard blood pressure cuff on the upper arm or leg. This therapy is hypothesized to protect against ischemia-reperfusion injury by cellular signaling between the remote site (limb) and the target organ (heart) through humoral or neuronal protective signal transfer. Although the mechanisms of RIC are unclear, it is thought to target several mediators of ischemia-reperfusion injury and may therefore be a more effective therapeutic strategy than those that target a single pathway.

### 1.2 Investigational Device

The autoRIC® (CellAegis Devices, Inc., Toronto, Ontario) is the only automated device currently available to deliver RIC for acute conditions. With timed inflations and deflations of an arm cuff, it automatically delivers four RIC cycles of five minutes of pressure at 200 mm Hg followed by five minutes of no pressure for a total 40-min treatment period. The autoRIC® has CE Mark certification in Europe and Health Canada approval to administer RIC therapy in adult patients with acute MI and those undergoing cardiothoracic interventions or surgery; the device is however limited to investigational use in the U.S. (<http://www.cellaeisdDevices.com/product.html> accessed May 9, 2017).

The autoRIC® system (Figure 1) consists of a rechargeable, reusable control unit that clicks into a one-time use, disposable applicator cuff and inflates and deflates the cuff to a preset pressure of 200 mm Hg on a timer. The applicator cuffs come in three adult sizes to accommodate arm circumferences ranging from 22 to 44 cm. A stand-alone charger for the control unit uses a standard AC adapter and can be wall mounted. The autoRIC® is compliant with international safety and

Figure 1. CellAegis' autoRIC® Device

performance standards for medical devices and electrical equipment including particular requirements for automated non-invasive sphygmomanometers (IEC 80601-2-30:2009).

### **1.3 Preclinical Data**

In 1986, Murry et al. first described ischemic conditioning in dogs, in which four 5-min occlusions of the circumflex coronary artery separated by 5-min episodes of reperfusion before a sustained occlusion limited myocardial infarct size to 25% of that observed in the control group. Dickson et al. demonstrated *remote* ischemic conditioning reduces infarct size with the transfer of coronary effluent from a preconditioned donor rabbit heart to an acceptor rabbit heart by transfusion. In 2002, Kharbanda et al. showed transient lower limb ischemia (four 5-min cycles) in pigs prior to a myocardial infarction substantially reduced infarct size. These researchers also demonstrated that the RIC response could be induced in humans non-invasively by simply inflating a standard blood pressure cuff around the upper arm to 200 mm Hg of pressure with three cycles of five minutes inflated and five minutes deflated. These and other preclinical studies provide convincing evidence of the existence of ischemia-reperfusion injury and suggest that ischemic conditioning has significant promise to prevent lethal reperfusion injury in humans.

### **1.4 Clinical Data to Date**

Prior randomized controlled trials (RCTs) have shown the benefit of RIC in several clinical applications, including reducing myocardial and renal injury in patients undergoing coronary artery bypass graft (CABG) surgery, abdominal aortic aneurysm surgery, and elective PCI. However, some clinical studies found null findings with RIC in these settings. Possible explanations for these null findings include differences in study design, inclusion criteria, and concomitant medications that could mitigate the effects of RIC. Recently, two large multi-center RCTs, conducted in the United Kingdom and Germany, failed to show a benefit of RIC on clinical outcomes. Garratt, et al. suggest one possible reason for the lack of clinical efficacy of RIC in recent large multi-center RCTs in patients undergoing *elective* CABG surgery is that the anesthetic drug propofol may inhibit signal transduction in response to the remote ischemia. They, among others, call for further clinical investigations in populations that may derive the most benefit from RIC, namely acute ST-segment elevation myocardial infarction (STEMI) patients undergoing *emergent* PCI.

Existing evidence on clinical efficacy suggests RIC is a promising adjunct to PCI in STEMI patients. Botker et al. conducted a randomized trial of RIC administered in the prehospital setting among 333 STEMI patients in Denmark in which they found RIC was feasible to implement in the ambulance and safely improved myocardial salvage 30 days after PCI. In a subgroup of left anterior descending STEMIs, myocardial salvage further increased, and left ventricular function was also significantly improved at 30 days. Two smaller randomized studies in STEMI patients undergoing primary PCI found RIC had beneficial effects on ST-segment resolution, cardiac enzymes, and other intermediate outcomes. In a post hoc analysis of the Danish trial, Sloth et al. found the RIC plus PCI group, compared to PCI only, had half the 4-year risk of the primary composite endpoint of major adverse cardiovascular events including all-cause mortality (HR=0.49, 95% CI 0.27-0.89). A recent meta-analysis synthesized results from four randomized studies that reported clinical endpoints and found major cardiovascular risk was significantly lower in patients receiving RIC + PCI compared PCI only (RR=0.57, 95% CI 0.40-0.82). Patient recruitment is underway for two large, multi-center clinical efficacy trials of RIC, administered with the autoRIC® device, in STEMI patients undergoing primary PCI (CONDI2 [NCT01857414](#) and ERIC-PPCI [NCT02342522](#)). However, even if these European and UK trials establish the efficacy of RIC in these patients, further U.S.-based research will be necessary to demonstrate effectiveness and facilitate implementation in U.S. emergency cardiac care systems.

## **1.5 Study Rationale**

Emergency medical services (EMS) play a key role in regional systems of STEMI care in the U.S. With proper training and patient care protocols, paramedics can perform and interpret 12-lead electrocardiogram (ECG) for STEMI in the field and directly transport suspected STEMI patients to a PCI-capable hospital, which has been shown to reduce delays to treatment and improve outcomes. Based on the findings from the Danish trial, EMS is a promising setting for field administration of RIC in acute MI patients prior to hospital arrival. There are however important differences in the provision of EMS between European countries like Denmark and the U.S. While EMS care in European countries is often provided by emergency physicians and have a culture of treating patients at the scene, ambulances in the U.S. are staffed with paramedics who are trained to prioritize timely transport to the hospital. Additional U.S.-based research of RIC is needed to elucidate the influence of these personnel and system factors and inform design decisions for future U.S.-based clinical studies that build on the completed trial from Denmark and the other European trials currently underway.

A recent feasibility study of administering RIC in patients with STEMI during U.S. air medical transports showed 84% of patients had at least three cycles of RIC completed. In this multi-state region, the air medical crew was typically a paramedic and nurse team, which made timed, manual cuff inflations and deflations feasible. However, the vast majority of acute MI patients in the U.S. are transported by ground ambulance, not by air, with care provided by a single paramedic. An automated device, such as the autoRIC®, could prevent delays or interruptions in care and eliminate the need for dedicated personnel or ongoing provider attention. Further study of EMS use of an automated device is needed to inform the design and optimize methods for a future U.S.-based trial of the clinical efficacy of RIC administered during ground ambulance transport.

## **1.6 Dose Rationale and Risk/Benefits**

In previously published clinical studies, one cycle of RIC has typically been five minutes of upper arm ischemia, induced by inflating a cuff to 200 mm Hg, followed by five minutes of reperfusion by deflating the cuff. Each 10-min cycle is repeated four times. This dosing regimen was followed in recently completed clinical trials, and is being used in the ongoing CONDI2 ([NCT01857414](#)) and ERIC-PPCI ([NCT02342522](#)) trials. Our study protocol will therefore administer RIC in accordance with these studies using the autoRIC® device, which automates the process.

Based on previous studies, RIC is a safe procedure with minimal risk to subjects across various settings and patient populations. From the Danish trial in which RIC was administered in STEMI patients in the ambulance prior to hospital arrival, Botker et al. reported no local adverse effects, such as pain or thrombophlebitis. In two large RCTs in patients undergoing CABG surgery, one observed no adverse events related to RIC; the other found 5% of the RIC intervention group experienced skin petechiae or arm weakness or altered sensation although none had long-term effects. In a U.S. study of RIC during air medical transport of STEMI patients, only 2% of patients stopped RIC due to discomfort.

Published studies of the autoRIC® device support the safety of this specific device for administering RIC. Two previous studies used this specific automated device to investigate the effect of RIC on coagulation, platelet function, and fibrinolysis in small samples of healthy male volunteers and patients with chronic heart failure. Neither study reported any complications or adverse events related to RIC or the device itself. However, neither study directly evaluated risks to subjects or studied the device in an emergency care setting.

Given the benign nature of the RIC procedure, no serious adverse events are expected as a result of the device. However, the device may result in non-serious adverse events, such as minor arm discomfort, temporary discoloration of the arm or hand, and minor skin bruising or abrasions on the upper arm. These anticipated risks are not expected to have long term consequences and are reasonable in relation to the knowledge gained on the feasibility of RIC and optimal methods for a full-scale clinical trial to help establish long-term benefits.

## 2 Study Objectives

The overall purpose of this pilot study is to assess the feasibility of the delivery of RIC by EMS in the prehospital setting. To this end, we will conduct a single-arm study of the standard RIC procedure (i.e., up to four cycles of alternating 5-min inflation and 5-min deflation) administered by Orange County (North Carolina) Emergency Services in 50 patients experiencing chest pain or other symptom consistent with cardiac etiology. The investigational autoRIC® device will be initiated by paramedics during ambulance transport, and automated RIC cycles will continue through emergency department (ED) arrival and stay. This pilot study will address the following objectives:

### 2.1 Primary Objective

Examine the duration of RIC administered in patients having the procedure initiated in the prehospital setting

*Hypothesis: Four cycles of RIC will be completed in at least 80% of patients having the procedure initiated.*

### 2.2 Secondary Objectives

The following secondary objectives will inform the design and optimize methods for a future clinical trial:

1. Evaluate patient enrollment and study protocol efficiency, i.e. patient eligibility and participation rates, times to screen, recruit and start the autoRIC® device
2. Assess acceptability of the study protocol by paramedics
3. Determine patient tolerability of the RIC procedure and describe related risks and discomforts

[figure not shown]
## 3 Study Design

### 3.1 General Design

This single-arm, open-label pilot study will enroll 50 patients experiencing chest pain or anginal equivalent symptom requiring a 9-1-1 response to incident scene and ground ambulance transport by Orange County Emergency Services (OCES), the primary EMS provider in the county. Eligible patients will be  $\geq 18$  years of age and be transported to the University of North Carolina (UNC) Medical Center, an accredited chest pain center. For this pilot study, patients suspected of STEMI based on the prehospital ECG and thus requiring urgent intervention in the cardiac catheterization lab will be excluded. Detailed subject selection criteria are described in Section 4.

The following diagram (Figure 2) illustrates the overall flow of patient enrollment and major procedural steps during ambulance transport and ED stay.

**Figure 2. Diagram of Patient Enrollment and Study Procedures**

 Although high risk STEMI patients hold the most promise for therapeutic benefit, the aims of this study surrounding feasibility of prehospital RIC can be addressed with a low risk population. By using chest pain patients not suspected of STEMI, we will simulate the prehospital setting expected for an efficacy trial of RIC while allowing adequate time to interview patients in the ED.

### **3.2 Primary Outcomes**

To assess the feasibility of delivering RIC in the prehospital setting, the primary endpoint will be the completion of 4 cycles of RIC without interruption using the autoRIC® device. We will also examine total time (in minutes) and number of cycles that RIC was administered.

### **3.3 Secondary Outcomes**

Secondary Objective #1: Patient enrollment and protocol efficiency

- a) Eligibility and participation rates and corresponding reasons for ineligibility and refusal
- b) Timing of study procedures
  - i) Time to onset of transport from initial arrival on scene
  - ii) Time to start screening from onset of transport
  - iii) Time to screen, whether eligible or not
  - iv) Time to recruit, whether enrolled or not
  - v) Time to start the autoRIC® device once consent is obtained

Secondary Objective #2: Paramedic acceptability

- a) Paramedics' feedback on the delivery of RIC and other study procedures

Secondary Objective #3: Patient tolerability

- a) Documentation of anticipated adverse events including RIC discontinuation due to discomfort
- b) Patients' experiences while undergoing the RIC procedure

## **4 Subject Selection and Withdrawal**

### **4.1 Inclusion Criteria**

Eligible patients will meet the following criteria:

1. Requiring 9-1-1 response to scene
2. At least 18 years of age
3. Experiencing non-traumatic chest pain or anginal equivalent symptom, as defined in OCES "Chest Pain: Cardiac and STEMI" patient care protocol (see Appendix A)
4. Not meeting EMS criteria for a suspected STEMI based on prehospital ECG
5. Systolic blood pressure (SBP) between 100-180 mm Hg
6. Designated for ambulance transport to UNC Medical Center (Chapel Hill, NC)
7. Capable of providing informed consent

### **4.2 Exclusion Criteria**

The following exclusions will be made in the prehospital setting and confirmed prior to recruitment:

1. Unconscious or otherwise in critical condition
2. Lacking capacity to consent to the study
3. Non-English speaking

---

 Does not include non-9-1-1 responses such as interfacility transfers and non-urgent medical transports

 Includes pain in other location suggesting cardiac etiology such as arm, shoulder, neck, or jaw; dyspnea; diaphoresis; nausea/vomiting; or dizziness

 Defined as 1 mm or greater ST segment elevation in at least 2 contiguous leads or otherwise prompting a prehospital STEMI alert or activation of the cardiac catheterization laboratory

 As judged by study paramedic and study coordinator

[figure not shown]
4. Pre-existing condition precluding blood pressure check or use of the autoRIC® at the discretion of the provider or listed here:
  - a. Paresis of upper limb
  - b. Pre-existing traumatic injury to arm
  - c. Presence of an arteriovenous shunt for dialysis
  - d. Prior mastectomy
  - e. Existing peripheral inserted central catheter line
  - f. Arm edema or other indication of upper extremity thrombosis
5. Serial ECG evidence of evolving STEMI

#### 4.3 Subject Recruitment and Screening

Two full-time OCES ground ambulance units that provide advanced life support (ALS) services to the southern part of Orange County and typically transport to UNC Medical Center will be used for this study. Paramedics assigned to these units will be responsible for assessing and screening patients during the enrollment period from 6am-6pm, Monday-Friday. So that arrival to the UNC ED is not delayed, screening and recruitment will not begin until the patient is en route to the hospital and given usual care, at the discretion of the paramedic. Paramedics will assess the patients' capacity to consent for the study following their usual approach to assessing patients' capacity to make medical decisions, e.g. accept or refuse treatment.

In a two-stage screening and recruitment process (Figure 3), the study paramedic will first assess and determine whether the patient meets all eligibility criteria. If the patient is not eligible, the paramedic will document the primary reason(s) on a screener form. If the patient is eligible, the paramedic, using a suggested script (see Appendix B), will offer the patient an opportunity to learn more about the study by telephone call with a study coordinator (SC). If the patient agrees, the paramedic will hand the patient a study information sheet (see Appendix C) and will call the SC or back-up key study personnel using a dedicated cellular telephone. In the second screening stage, the SC will confirm with the paramedic that the patient is eligible. Then the patient will be handed the telephone. The SC, following a script (see Appendix B), will provide basic information about the purpose of the study, RIC procedure, and risks and benefits of participating and will answer any questions that patient may have. To assess consent capacity, the SC will ask the patient to describe the RIC procedure and whether study participation will have any effect on medical care received. A patient with capacity to consent will be invited to participate. If the patient responds in the affirmative, this will be considered verbal consent, and the SC will instruct the paramedics to apply and start the autoRIC® device. This telephonic method to obtain consent in the field is based on a strategy developed and tested in prior prehospital trials by Saver et al.

Figure 3. Flow chart of recruitment and enrollment

When the patient and paramedic crew arrive to the ED, providers in the ED will first provide standard care. The SC will collect study forms and other documentation from the paramedic. Once initial care (e.g., provider assessment, repeat ECG, lab draws) is completed and the patient is placed under observation for further work-up, the SC will approach the patient, with approval from the treating physician, to complete the full informed consent process and describe additional data collection including medical record review and abstraction and collection and storage of blood samples for future testing. The SC will assess comprehension based on the patient's ability to restate key study objectives and procedures and anticipated risks and benefits. If the patient consents, both SC and patient will sign two copies of the informed consent form (see Appendix D), one for study documentation and the other for the patient. If the patient refuses, RIC will be stopped and data collected up to that point will be de-identified and retained to address primary and secondary study objectives.

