## 6.2 Emergency Department

The SC will meet the paramedic team and patient in the ED. At this point, the paramedic will hand over the CRF to the SC and transfer study responsibilities, including safety and adverse event reporting. After initial ED care and while the patient is under observation and awaiting further work-up, the SC will complete the full informed consent process. This process may occur while the RIC procedure is still in progress. Although the study intervention is already started, the subject will have the opportunity to decline participation in the patient interview; access to medical records and other clinical data; and collection and storage of blood specimens for future testing. The SC will assess comprehension of consent by asking the subject to describe the purpose of the study, foreseeable risks and benefits of study participation, the possibility of unanticipated risks, and other elements of informed consent. No additional study procedures will occur until the consent process is complete and both patient and SC sign necessary consent forms.

After consent is obtained, a blood sample of 15 mL will be collected by Department of Emergency Medicine clinical research staff using existing venous access. When possible, this sample will be obtained with other blood draws taken as part of usual care. Blood for plasma will be collected using an EDTA tube (e.g., BD Vacutainer® plastic blood collection tube). Tubes will be labeled with the date and time of collection and the unique subject ID but no other identifiers. Specimens will be prepared according to standard procedures for separating plasma and will be stored in a -80 °C freezer located in a locked area in the department's research laboratory. No blood testing or analyses will be done under this protocol. In future studies, these samples may be used to investigate biomarkers and molecular pathways involved in the mechanism(s) of RIC.

Using an interview guide, the SC will elicit patient feedback on undergoing the RIC procedure (e.g., "what did it feel like?", "how would you describe to someone else?"). The SC will note subject responses in the CRF.

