## 6.3 Post-Visit

There will not be any post-ED visits required of the subject. All additional study data collected following the study visit will be obtained by the SC or other study personnel via retrospective chart review and will not require subject interaction. Subjects will however be contacted after 48 hours, either by telephone or in-person depending on location, to assess for adverse events related to study participation.

Following the study visit, the SC will enter data from the CRF into a secure, web-based database (Research Electronic Data Capture, REDCap). Additional relevant clinical data from the subject's medical record (e.g. medical history, diagnoses, and lab results) and the EMS patient care report will also be abstracted and entered into the database. Furthermore, automatic reports from the EMS agency's LIFEPAK® 12 cardiac monitor will be retrieved and saved for potential additional analyses of vital signs and ECG patterns. Frozen plasma specimens may be thawed and tested in future research exploring mechanisms of RIC.

[figure not shown]

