## 7.3 Subject Population for Analysis

For both primary and secondary objectives, any subject consented and enrolled to receive RIC will be analyzed.

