### **Adverse Event Reporting Period**

The study period during which adverse events must be reported will start at the time of verbal consent, include the 40-min RIC procedure, and conclude when the SC completes study procedures in the ED. A subject follow-up contact will be made at 48 hours to assess for adverse events. If a subject expresses RIC-related health concerns at any time, s/he will be connected to a study physician for a telephone assessment and triage which will include a determination of whether re-evaluation in the ED is needed.

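### Do patients who refuse full consent in the emergency department leave a gap in the analyses that the plan must close?

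*Combined protocol and SAP*

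**What the plan says.** Consent has two stages. Section 4.3 lets RIC begin once the patient agrees by telephone; the signed form follows in the ED. Section 6.2 says of the signing step: "This process may occur while the RIC procedure is still in progress". A refusal can therefore fall before or after the fourth cycle.

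On refusal, section 4.3 stops RIC and provides that "data collected up to that point will be de-identified and retained to address primary and secondary study objectives". Section 7.3 defines the analysis set: "For both primary and secondary objectives, any subject consented and enrolled to receive RIC will be analyzed". Section 7.2 takes all subjects who receive RIC as the denominator of the primary proportion.

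What can be collected afterwards depends on the signature. Section 6.2 states: "No additional study procedures will occur until the consent process is complete and both patient and SC sign necessary consent forms". It also lets the subject "decline participation in the patient interview; access to medical records and other clinical data; and collection and storage of blood specimens". Section 6.3 places medical history in the later chart review, where data from the "medical record (e.g. medical history, diagnoses, and lab results) and the EMS patient care report will also be abstracted".

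On safety, section 6.3 says: "Subjects will however be contacted after 48 hours, either by telephone or in-person depending on location, to assess for adverse events". Section 8.1 (Adverse Event Reporting Period) repeats it: "A subject follow-up contact will be made at 48 hours to assess for adverse events". Neither sentence mentions patients who refused.

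**The concern.** Read together, these sections keep refusers in every analysis while closing off several sources of their data. Three things appear to be missing.

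- **Interview.** Secondary outcome 3b in section 3.3 (patients' experiences) has no entry for a refuser.
- **Medical history.** Section 7.2 compares completers with non-completers on medical history. The only source the documents name for it is the record abstraction, which needs the ED consent. A patient who refuses during the run is always a non-completer, so the loss falls on the smaller group.
- **48-hour contact.** It is written for subjects without exception, yet section 4.3 ends the data at refusal and de-identifies them.

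Section 7.2 names no separate denominators. If refusers had a worse experience than signers, which is an assumption, tolerability would look better than it was. The non-completers would also be under-described in results meant to inform a future trial.

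**Working it through.** **1. The plan's own figure.** Section 7.1 gives n = 50, completion 0.80 and a 95% half width of 0.11.

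1.96 × √(0.80 × 0.20 / 50) = 0.111.

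The figure reproduces. Refusers stay in the denominator of 50, so they cost it no sample size.

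**2. Is the primary endpoint known for a refuser?** Yes.

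- Section 5.5 records start and stop times, and the cycles completed if the device is stopped early for any reason.
- Section 4.4.1 counts early discontinuation towards the primary endpoint.
- A refusal during the run is therefore a non-completion. A refusal after the fourth cycle leaves a completer a completer.

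No scoring rule is missing.

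**3. What is held for a refuser, and what is not.**

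| Item | Held? | Where |
|---|---|---|
| Cycles, start and stop times | Yes | 5.5 |
| Reason for stopping or withdrawing | Yes | 4.4.1, 4.4.2 |
| Screener, time points and paramedic observations | Yes | 6.1 |
| Paramedic medications | Yes | 5.6 |
| Adverse events from verbal consent up to refusal | Yes | 8.1, 6.1, 4.3 |
| Interview (outcome 3b) | No | 6.2 |
| Abstracted medical history | No | 6.2, 6.3 |
| 48-hour contact | Not stated | 6.3, 8.1 against 4.3, 4.4.2 |

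**4. Size.** The documents give no refusal rate. Let r be the number who refuse during the run (assumed).

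*Overall completion fixed at 40 of 50.* There are 10 non-completers, of whom 10 − r have medical history: 9, 8 and 6 for r = 1, 2 and 4. The share without history is 10%, 20% and 40%.

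*Instead, 80% of signers complete.* Non-completers number 50 − 0.80 × (50 − r). For r = 4 this is 50 − 36.8 = 13.2, and the share without history is 4 / 13.2 = 30%.

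One refusal after the run, at 40 completers, removes history for 1/40 = 2.5% of them.

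*What r = 4 could do to one characteristic.* Suppose 3 of the 6 non-completers with history have it. Across all 10, the proportion lies between 3/10 = 30% and (3 + 4)/10 = 70%. For comparison, with complete data on 10 and an observed 50%, the 95% half width is 1.96 × √(0.50 × 0.50 / 10) = 0.31, giving 19% to 81%. Sampling error in a group of 10 already exceeds this range from missing data.

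*Precision of outputs based on signers.* The largest denominator is 50 − r. At a proportion of 0.80 the half width is 0.112 for 49, 0.113 for 48 and 1.96 × √(0.16 / 46) = 0.116 for 46, against 0.111 for 50.

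**5. The 48-hour contact.** No sentence includes or exempts refusers.

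- Section 4.4.2, on withdrawn subjects, says the objectives need no follow-up beyond the ED stay.
- Section 8.1 (Post-study Adverse Event) follows unresolved events until they resolve, but also allows follow-up to end when the subject is lost or the event is otherwise explained.
- Section 8.2 still requires later serious events that may be related to be recorded and reported.
- Section 3.3 names no outcome measured at 48 hours.

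The text leaves an exception unstated. It does not set one required outcome against another.

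**The case for a change.** The strongest case for a change is that the loss is not random. Refusals during the run fall only among non-completers, and tolerability is an objective of the pilot. The ED interview also matters to the design: the footnote in section 3.1 justifies the non-STEMI population partly by the time it leaves for interviewing. A few words on denominators would be cheap, and the uncertainty about the 48-hour contact arises with a single refuser.

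The direction of the loss stands, and so does the silence on the 48-hour contact. The case for amending is weaker.

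- The interview is open-ended and analyzed for themes (sections 6.2 and 7.2). Any subject may decline it, so incomplete coverage is inherent in voluntary interviewing. Best-case and worst-case bounds do not apply to themes.
- Discontinuation for discomfort (outcome 3a) and the reasons for stopping are collected for refusers, so tolerability is not left to signers alone.
- One might set 0 of 46 with an event (upper 95% limit 7.7%) against 4 of 50 (8.0%, 2.2% to 19.2%) if four refusers all had one. That treats refusers as unobserved. In fact their events are reportable from verbal consent and kept up to refusal, which covers the time the cuff was running.
- Asking a tolerability question before the ED consent discussion would run against section 6.2 and the written-consent requirement in section 11.
- Naming every ED refusal as a non-completion would misclassify patients who refuse after the fourth cycle.

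Section 6.2 also lets a subject decline single components without saying what then happens to RIC in progress, whereas section 4.3 stops it on refusal. Those passages, and those on the 48-hour contact, are for the sponsor-investigator and the IRB to read together; I propose no rule. Either way, section 5.5 records the cycles delivered, so the primary score is determined.

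**Conclusion.** The observation is accurate, but no change to the plan is needed. The primary proportion is complete for refusers and keeps its planned half width of 0.11. The remaining gap is missing detail that analysts fill as a matter of course: give each descriptive result with the number who supplied it, note that interview and medical-history results come from those who signed, and count ED refusals among the reasons for stopping. Keeping every subject in the analysis set does not promise complete data on every variable, and losing record access after a refusal is the price of respecting it.

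The size is conditional. It rests on an assumed number of refusals during the run, which may be nil, and on the plan's 80% of 50. Each such refusal then removes history for one of about 10 non-completers, in a comparison made without tests. Any bias in tolerability further requires that refusers fared worse than signers, which the documents neither support nor exclude. Whether the 48-hour contact applies after refusal is a question of conduct and consent that alters no outcome named in section 3.3.
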